7.1. Study Subjects

7.1.1. Disposition of Subjects

Summaries of subject accountability will be created for subjects enrolled in the US Clinical Trial and the International Clinical Trial as well as two cohorts combined. Subjects discontinued or dropped off from the study will be listed by last day in study and reason for discontinuation.

7.1.2. Clinical Investigation Plan (CIP) Deviations

Clinical Investigation Plan (CIP) deviations will be reported and summarized. Major deviations will include violation of informed consent and/or inclusion/exclusion criteria.

7.1.3. Analysis Sets

Analysis set to be used for each endpoint analysis will consist of all subjects who were enrolled. The subject will only be considered enrolled when arterial access is established and an attempt to introduce the Valiant Evo Thoracic Stent Graft is made.

Valiant Evo US Clinical Trial Statistical Analysis Plan Version 2.0 Nov 1, 2017

This document is electronically controlled. Printed copies are considered uncontrolled.

7.2. General Methodology

In general, qualitative parameters will be described by their distribution frequencies; quantitative parameters will be described by their mean, standard deviation, minimum, maximum, median, and number of subjects with assessable data.

For events such as adverse events (AE), deaths and secondary procedures, that can occur or are observed at any time during the study, no time window will be applied. For such events, an event that occurs "within 1 month or 30 days" is an event that takes place between Days 0 to 30, inclusive. Similarly, an event that occurs "within 12 months or 365 days" is an event occurring between Day 0 to Day 365, inclusive. Date of event onset will be used to determine when the event occurred. Day 0 is referring to the day of index procedure.

For image-based assessments, such as stent-graft endoleak, patency, and other observations, the following time windows will be applied for by-visit data summaries:

Study Visit	Target Day	Time Window
Implant	Day 0	Day 0
1 Month	Day 30	1 – 90 days
6 Months	Day 183	91 – 304 days
12 Months	Day 365	305 – 548 days
24 Months	Day 730	549 – 913 days
36 Months	Day 1095	914 – 1278 days
48 Months	Day 1460	1279 – 1643 Days
60 Months	Day 1825	1644 – 2009 days

Table 3: Time Windows for Statistical Analyses

Unless otherwise specified, if different type of images are used and have different finding in the same time window, the imaging technique and sensitivity matrix (CIP Appendix L.3, also see Table 4 below) will be applied. Finding from higher visibility image will be used for analysis. If there are two or more assessments in the same time window, then the assessment closest to the target day will be used in the analysis of event rate at a given time point.

Valiant Evo US Clinical Trial Statistical Analysis Plan

Version 2.0 Nov 1, 2017

This document is electronically controlled. Printed copies are considered uncontrolled.

Anatomy/Stent Graft Issue Detected	CT with contrast	CT without contrast	MRI with contrast	MRI without contrast	Angiogram/, Aortogram, and Arteriogram
Diameter and Length	1	2	1	2	3
Stent graft migration	1	2	1	2	2-3
Stent graft fracture	2	3	2	3	2-3
Stent graft kinking	2	3	2	3	2-3
Collapse of stent graft	2	3	2	3	2-3
Stent graft twisting	2	3	2	3	2-3
Stent graft patency	1	4	1	4	2-3
Endoleaks	1	4	1	4	2-3
False lumen perfusion	1	4	1	4	2-3
Occlusion	1	4	1	4	2-3
Stenosis	1	4	1	4	2-3
Stent Graft Fabric Defect	1	4	1	4	2-3
1= Highly visible	2 = visible	3 = Nc	t very visible	(potential artifact	s) 4 = Invisible

Table 4: Imaging Matrix

Statistical analyses for this study will be performed using the Statistical Analysis System (SAS) for Windows (Version 9.1 or higher) or other widely-accepted statistical or graphical software.

7.3. Data Pooling

The data poolability of subjects enrolled in the Valiant Evo US Clinical Trial and subjects enrolled in the Valiant Evo International Clinical Trial is assumed given that both study protocols will be similar with respect to, inclusion/exclusion criteria, clinical treatment, definitions of clinical events, one data monitoring plan, Data

Valiant Evo US Clinical Trial Statistical Analysis Plan Version 2.0 Nov 1, 2017

This document is electronically controlled. Printed copies are considered uncontrolled.

Monitoring Committee (DMC), Clinical Event Committee (CEC), Independent Physician Reviewer (IPR) and core imaging laboratory.

At the data analysis stage, the data poolability will be reviewed for the primary endpoint. Results from Valiant Evo US Clinical Trial and Valiant Evo International Clinical Trial subjects will be presented separately for clinical review as well as tested using a Chi-square test.

A poolability analysis among geographies/investigational sites will be assessed descriptively for the primary endpoints by geographic regions. Small investigational sites (less than 5 subjects) will be grouped with other nearby sites for the by-region analysis.

7.4. Handling of Missing Data and Dropouts

During statistical analysis, imputation of missing data will not be performed except for data related to the onset date of an adverse event or a death. In cases where the onset date of an event or a death is incomplete and unresolvable via data query, the 15th day of the known month or July 1st of the known year will be used.

Sensitivity analysis using tipping point method may be performed, as needed, to assess the impact of missing data for the primary endpoint.

7.5. Adjustments for Multiple Comparisons

One hypothesis test on the primary study endpoint will be performed at the time of PMA submission. Therefore, there is no multiple comparisons/multiplicity issue.

When the post-approval analysis is carried out, no multiplicity adjustment is needed due to the fact that the post-approval analysis is conditioning on the PMA approval.

7.6. Demographic and Other Baseline Characteristics

Descriptive statistics will be provided for demographic (age, gender, and race) and other baseline characteristic variables such as medical history and baseline thoracic aorta measurements. Note that race will be summarized for subjects enrolled in the US only, since collection of race and ethnicity data may not be allowed outside the US as per local law and regulation.

7.7. Treatment Characteristics

The following acute procedural observations and clinical utility measures will be analyzed using descriptive statistics:

- Mean duration (min) of procedure
- Proportion of subjects who underwent general anesthesia
- Proportion of subjects who underwent percutaneous access
- Proportion of subjects requiring blood transfusions

Valiant Evo US Clinical Trial Statistical Analysis Plan Version 2.0 Nov 1, 2017

This document is electronically controlled. Printed copies are considered uncontrolled.

- Mean number of units of blood transfused, if required
- Mean volume (cc) of estimated blood loss
- Mean length of time (hours) in intensive care unit
- Mean length of time (days) of hospital stay (from the index procedure to hospital discharge)

Study device disposition will be summarized by type and size. Number of study devices used on each subject will be analyzed descriptively.

7.8. Interim Analyses

No interim analysis intended for sample size recalculation is planned prior to the PMA submission.

Data reports will be generated for Data Monitoring Committee (DMC) review during the trial. A design dossier including clinical evaluation of the Valiant Evo Stent Graft System will be created for the CE mark submission. However, there is no plan to modify the Valiant Evo US Clinical Trial based on these reports.

7.9. Evaluation of Objectives

Primary Endpoint

The primary objective will be assessed by the composite safety and effectiveness endpoint that is based on the proportion of subjects who experienced:

- (a) Access and/or deployment failures; and/or
- (b) Major device effects (MDE) within 30 days post index procedure

MDEs include the occurrence of any of the following:

- Device-related secondary procedures
- Device-related mortality
- Conversion to open surgery
- Thoracic aortic aneurysm rupture

Detailed definitions of MDEs are defined in Clinical Investigational Plan Appendix L.5.

The primary study endpoint will be tested against a performance goal of 16% at 30 days:

 $H_0: p \ge 16\%$ vs. $H_a: p < 16\%$,

where p denotes the true event rate of primary study endpoint in the target population. If the null hypothesis

Valiant Evo US Clinical Trial Statistical Analysis Plan Version 2.0 Nov 1, 2017

This document is electronically controlled. Printed copies are considered uncontrolled.

(H₀) is rejected at the one-sided 0.025 statistical significance level, it is considered that the performance goal for the primary endpoint has been reached.

The analysis set of all enrolled subjects will be used for the analysis. The primary study endpoint is a dichotomous study outcome; hence, an exact method based on the binomial distribution will be used for the hypothesis testing.

Primary Endpoint Calculation:

A subject will be a failure on the primary endpoint if the subject either failed on access/deployment or had an MDE within 30 days. A subject will be a success on the primary endpoint if the subject is confirmed for access and deployment success as well as free from MDE. The failure rate of the primary endpoint is the percent of failures in all the evaluable subjects for the endpoint, i.e., in total number of failures and successes. Note that a subject who had an MDE within 30 days is one of the subjects in m as defined below. A subject who is free from MDE is one of the subjects in k as defined below.

MDE Rate Calculation:

All MDEs will be adjudicated by the Clinical Event Committee (CEC) per study protocol. MDE rate will be calculated as follows (Table 5):

MDE rate = m/(m + k)	Within 30 Days	Within 183 Days	Within 365 Days
m = No. of Subjects Who Had MDE(s)	No. of subjects who had at least one MDE with onset day from Day 0 to Day 30, inclusive.	No. of subjects who had at least one MDE with onset day from Day 0 to Day 183, inclusive.	No. of subjects who had at least one MDE with onset day from Day 0 to Day 365, inclusive.
k = No. of Subjects Who Had No MDE	No. of subjects who have been in study for at least 1 day and without an MDE.	No. of subjects who have been in study for at least 91 days and without an MDE.	No. of subjects who have been in study for at least 305 days and without an MDE.

Table 5: MDE Rate Calculation:

If a subject is early terminated from the study, the last day that the subject has been seen will be the duration in study, which can be the day of last follow-up, last imaging taken, an AE reported, or withdrawal from the study. If a subject is still in the study, the duration in study will be the time from index procedure to the cut off day that the database is locked or data snapshot is taken.

Subgroup analyses by-sex, by-race (based on subjects enrolled in the US only, since collection of race and ethnicity data may not be allowed outside the US as per local law and regulation), FreeFlo versus Closed Web configuration as proximal component, percutaneous access versus non-percutaneous, and by-region/study site will be performed on the primary study endpoint using descriptive statistics and reviewed for

Valiant Evo US Clinical Trial Statistical Analysis Plan

Version 2.0 Nov 1, 2017

This document is electronically controlled. Printed copies are considered uncontrolled.

clinical significant difference.

Secondary Endpoints

30-day Secondary Endpoint

The following secondary endpoints will be evaluated within 30 days post treatment:

- Peri-operative mortality
- All adverse events (AE) within 30 days including:
 - Major Adverse Event(s) (MAE)
 - Serious Adverse Event(s) (SAE)
- Secondary procedures
- Loss of stent graft patency at 30 day visit based on imaging findings
- Endoleaks at 30 day visit based on imaging findings

Detailed definitions of MAEs are defined in the Clinical Investigational Plan Appendix L.2.2. MAEs will be identified using codes in the Medical Dictionary for Regulatory Activities (MedDRA) provided by the Medtronic Clinical Safety group.

6-month Secondary Endpoints:

The following secondary endpoints will be evaluated:

- All-cause mortality within 183 days
- Aneurysm-Related Mortality within 183 days
- MDEs within 183 days
- All AEs within 183 days including:
 - \circ MAEs
 - o SAEs
- Secondary procedures within 183 days
- Loss of stent graft patency within 6 months based on imaging findings
- Endoleaks at 6 months based on imaging findings

Valiant Evo US Clinical Trial Statistical Analysis Plan Version 2.0 Nov 1, 2017

This document is electronically controlled. Printed copies are considered uncontrolled.

- Stent graft migration at 6 months as compared to 1-month imaging
- Aneurysm expansion > 5mm at 6 months based on imaging findings relative to the 1-month visit

12-month Secondary Endpoints

The following secondary endpoints will be evaluated:

- All-cause mortality within 365 days
- Aneurysm-Related Mortality within 365 days
- MDEs within 365 days
- All AEs within 365 days including:
 - o MAEs
 - o SAEs
- Secondary procedures within 365 days
- Loss of stent graft patency within 12 months based on imaging findings
- Endoleaks at 12 months based on imaging findings
- Stent graft migration at 12 months as compared to 1-month imaging
- Aneurysm expansion > 5mm at 12 months based on imaging findings relative to the 1-month visit

Secondary endpoints are to be assessed beyond 12 months. The following secondary endpoints are to be evaluated at 24, 36, 48, and 60 months:

- All-cause mortality
- Aneurysm-Related Mortality
- MDEs
- All AEs and SAEs
- Secondary procedures
- Loss of stent graft patency based on site reported imaging findings
- Endoleaks based on site reported imaging findings

Valiant Evo US Clinical Trial Statistical Analysis Plan Version 2.0 Nov 1, 2017

This document is electronically controlled. Printed copies are considered uncontrolled.

- Stent graft migration as compared to 1-month imaging
- Aneurysm expansion > 5mm based on site reported imaging findings relative to the 1-month visit

Health-related quality of life outcomes are to be assessed at all scheduled follow-up visits using the EQ-5D questionnaire.

Stent graft migration will be determined by the core lab or site imaging case report from (CRF). Core lab assessment and site reported result will be analyzed separately. Aneurysm expansion will be calculated. When 1-month image is not available, the latest image taken prior to 1-month will be used for calculation.

Descriptive statistical analyses will be performed on secondary endpoints. No inferential statistical analysis is planned for secondary endpoints.

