Number of subjects	Globally, a total of 100 subjects will be concurrently enrolled in the United States and outside the United States to support the primary endpoints. Up to 50% of subject data used to support PMA approval may come from subjects enrolled at sites outside of the US under a separate CE Mark study protocol; called the Valiant Evo International Clinical Trial protocol. The primary endpoint analysis will be completed upon 87 evaluable subjects reaching the 30 day endpoint.
	The data obtained from these 87 evaluable subjects will be used to support PMA-S Approval of the Valiant Evo Thoracic Stent Graft System.
	The Valiant Evo US Clinical Trial protocol and Valiant Evo International Clinical Trial protocol will be identical with respect to the inclusion/exclusion criteria.
Number of Sites	The Valiant Evo Global Clinical program will be conducted at up to 37 sites worldwide, with at least 50% of the clinical sites coming from the United States.
Clinical Procedures and Follow Up Schedule	 Subjects require follow-up evaluations at the following time points: 1 month following the index procedure (30 ± 15 days) 6 months following the index procedure (183 ± 30 days) 12 months following the index procedure (365 ±60 days) 24 months following the index procedure (730 ± 60 days) 36 months following the index procedure (1095 ± 60 days) 48 months following the index procedure (1460 ± 60 days) 60 months following the index procedure (1825 ± 60 days)
	For subjects that re-consent to extended study follow up, the assessments as performed during the 12-month visit are to be repeated at 24, 36, 48 and 60 month visits.
Principal Investigator	[name] Director, Vascular Surgery Cedars-Sinai Medical Center [name]
Indications for Use	The Valiant Evo Thoracic Stent Graft System is indicated for the endovascular repair of fusiform aneurysms and saccular aneurysms/penetrating ulcers of the descending thoracic aorta (DTA) in patients having the appropriate anatomy including the following:
	Iliac or femoral artery access vessel morphology that is compatible with vascular access techniques, devices, or accessories
	 Nonaneurysmal aortic diameter from 16 mm to 42 mm Nonaneurysmal aortic proximal neck length ≥20 mm (for FreeFlo configuration) and ≥25 mm (for Closed Web configuration)

	Distal neck length ≥20 mm

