DATA	Screening / Baseline	Index Procedure	Hospital Discharge	1-Mo. F/U (±15 days)	6-Mo. F/U ^d (+ 30 days)	12-Mo. F/U (+ 60 days)	24, 36, 48 & 60-Mo. F/U (+ 60 days)
GENERAL							
Informed Consent	*						
Inclusion Criteria/ Exclusion Criteria	*						
Physical Examination	~			✓	>	~	✓
Medical History	✓						
Current Health Status and Risk Factors	√						
Device and Procedure Information		✓					
Pre-implant Adjunctive Procedures		✓					
Hospital Discharge Information			✓				
Adverse event assessment	√a	✓	✓	✓	√	✓	✓
EQ-5D questionnaire	✓			✓	✓	✓	✓
IMAGING							
CT/MRI with contrast ^b	√g			√c,e,g	√e.g	√e.g	√e,h
Angiography		√f					

^a In case of screen failures, investigators will be requested to enter safety information in the eCRF from time point of enrollment until time point of screen failure

^b CT evaluation may include "3-phase technique", volume studies, 3-D reconstruction, or computer-aided measurements

^c A CT/MRI with contrast acquired at discharge (or before Day 15) due to medical necessity may be used to meet the 1-month follow-up visit CT/MRI requirement if a CT/MRI with contrast cannot be obtained within the 1-month follow-up window due to the subject's health status based upon physician discretion.

^d For subjects enrolled in the Valiant Evo International Clinical Trial in European countries, a six month follow up visit is not required per protocol.

^e MRI with contrast may be used for those patients experiencing renal failure or who are otherwise unable to undergo contrast-enhanced CT scan, with Transesophageal echocardiography (TEE) being an additional option in the event of suboptimal MR imaging.

^f Required to complete Procedure eCRF but not expected to be submitted to Medtronic or Core Lab unless further analysis is needed.

g Imaging assessed by core lab.

^h Upon sponsor request, core lab analysis of imaging may be required.

F.4 Role of the sponsor's representatives

Sponsor's representatives may provide support as required for the clinical study, including technical support during implant. The sponsor representative is an experienced expert of device sizing, placement and the technical features of the device and will advise the implanting physician during the implant procedure if needed. The sponsor representative will not be involved actively during the placement and deployment of the Valiant Evo Thoracic Stent Graft System.

F.5 Source documents

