The Valiant Evo Global Clinical program will be conducted under both the Valiant Evo US Clinical Trial protocol and Valiant Evo International Clinical Trial protocol, and will enroll up to 37 sites worldwide. Inclusion will be halted at sites that reach the 20% inclusion cap. There will be no minimum number of subjects for a single investigational site. Globally, a total of 100 subjects will be concurrently enrolled in the United States and outside the United States to support the primary endpoints. Up to 50% of subject data used to support PMA approval may come from subjects enrolled at sites outside of the US under the Valiant Evo International Clinical Trial protocol.

The primary endpoint analysis will be completed upon 87 evaluable subjects reaching the 30 day endpoint. The data obtained from these 87 evaluable subjects will be used to support PMA-s Approval of the Valiant Evo Thoracic Stent Graft System and to support any other future Medtronic submissions to regulatory bodies.

Subjects enrolled under the Valiant Evo US Clinical Trial require follow-up evaluations at the following time points:

- 1 month following the index procedure (30 ± 15 days)
- 6 months following the index procedure (183 ± 30 days)
- 12 months following the index procedure (365 ±60 days)
- 24 months following the index procedure (730 ±60 days)
- 36 months following the index procedure (1095 ±60 days)

Valiant Evo US Clinical Trial Statistical Analysis Plan Version 2.0 Nov 1, 2017

This document is electronically controlled. Printed copies are considered uncontrolled.

- 48 months following the index procedure (1460 ±60 days)
- 60 months following the index procedure (1825 ±60 days)

Note that the 6-month follow up is not mandatory for subjects enrolled under the Valiant Evo International Clinical Trial protocol. Available 6-month follow-up data from the international trial will be used for analysis.

Subjects will be followed until the last subject enrolled has completed the 1 year follow-up visit or until PMA approval is obtained in the US (whatever is later), however, Medtronic will work with FDA to determine if longer term follow after PMA approval is required. A post-approval analysis of 1-year Major Device Event (MDE) rate is planned.

6. Determination of Sample Size

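### SAP 7.9 counts still-enrolled subjects as observed up to the data cut, so a subject with missed visits is scored MDE-free at 183 and 365 days without confirmed contact

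*SAP*

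**What the plan says.** SAP 7.9 defines the MDE rate as m/(m + k), where m counts subjects with an MDE and k counts subjects without one who meet a minimum duration in study. The minimums in Table 5 are:

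- 30 days: "No. of subjects who have been in study for at least 1 day and without an MDE"
- 183 days: "No. of subjects who have been in study for at least 91 days and without an MDE"
- 365 days: "No. of subjects who have been in study for at least 305 days and without an MDE"

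The text below Table 5 sets two clocks. For early-terminated subjects, "the last day that the subject has been seen will be the duration in study". For the rest: "If a subject is still in the study, the duration in study will be the time from index procedure to the cut off day" of the lock or snapshot. Entry to k requires no visit, call, image or record check.

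Three other provisions bear on this:

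- Protocol F.7.4 allows lost-to-follow-up status after three documented contact attempts but sets no deadline. F.7.3 records a last-known-alive date at a missed visit if one is obtained. The SAP duration rule does not use it.
- For European subjects, footnote d of protocol Table F-2 says "a six month follow up visit is not required per protocol". SAP section 5 states the exemption for the international trial as a whole.
- SAP 7.9 calculates mortality, secondary procedures, MAEs, SAEs, conversion and rupture through 1 year in the same way as Table 5.

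**The concern.** For subjects who leave, the SAP treats the last day seen as the end of observation. A silent subject who has not been exited gets more credit than that, and the SAP gives no reason. The minimums of 1, 91 and 305 days equal the opening days of the 1-, 6- and 12-month analysis windows in SAP Table 3. Under the cut-date clock, however, a subject passes 91 or 305 days by the calendar alone, whether or not anyone saw the subject in that window.

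The 365-day column matters most, because it feeds a hypothesis test: protocol C.3 and Appendix L.6 and SAP Table 2 set a 20% goal at one-sided 0.05. An event in an unseen subject that never reaches the database is scored as a success. Relative to full observation, the error can only reduce the observed rate and so favours passing.

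**Working it through.** **1. The plan's own figures.** Let c be the largest failure count with P(X ≤ c | n, goal) ≤ alpha, using the exact binomial.

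- 30 days (n = 87, goal 16%, alpha 0.025): c = 7; P(X ≤ 7 | 0.16) = 0.0233; P(X ≤ 8 | 0.16) = 0.0495. Power at 6% is 84.9%, against 85% stated.
- 1 year (n = 63, goal 20%, alpha 0.05): c = 7; exact alpha 0.0473. Power at 7.1% is 92.3%, against 92% stated.
- 1 year with all 100 enrolled subjects: c = 13; exact alpha 0.0469.

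**2. Which rule puts a subject without an MDE in k?** All three example subjects are still enrolled.

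| Subject | Column | SAP clock | Last contact, same minimum |
|---|---|---|---|
| Last seen Day 183, 12-month visit missed, cut Day 425 | 365 | 425 ≥ 305: in k | 183 < 305: out |
| Last seen Day 30, no 6-month visit required, cut Day 200 | 183 | 200 ≥ 91: in k | 30 < 91: out |
| Last seen Day 29, cut Day 40 | 30 | 40 ≥ 1: in k | 29 ≥ 1: still in k |

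At 183 and 365 days the cut-date clock decides. At 30 days it does not, because the 1-day minimum admits the subject on either clock. Raising that minimum to 30 days while keeping the cut-date clock would not exclude the third subject either (40 ≥ 30).

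Appendix L.6 places the 1-year analysis after the last subject's 12-month visit. If that visit is in window (Day 305 or later), every MDE-free subject not exited early has passed 305 days by then. The minimum then screens out only subjects who left early.

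**3. Size at 1 year.** The documents give neither u, the number of unseen subjects counted as MDE-free, nor s, the share of their events still captured. Both are assumptions. With a true rate of 20%,

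P(pass) = Σₓ P(X = x | u, 0.20·s) × P(Y ≤ c − x | N − u, 0.20).

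| N (c) | u | s = 0.85 | s = 0.5 | s = 0 |
|---|---|---|---|---|
| 100 (13) | 0 | 0.047 | 0.047 | 0.047 |
| 100 (13) | 10 | 0.054 | 0.075 | 0.115 |
| 63 (7) | 0 | 0.047 | 0.047 | 0.047 |
| 63 (7) | 10 | 0.057 | 0.085 | 0.142 |

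The planning rates, 6% by Day 30 and 7.1% by 1 year, suggest s of about 6/7.1 = 0.85 for subjects observed through Day 30. That is the mild end of the range.

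**4. Residual gap at 30 days.** Protocol Table F-1 allows the 1-month visit from Day 15 to Day 45. A visit on Day 15–29 leaves 1 to 15 days uncovered. If visits were uniform over the 31 days (an assumption), 15/31 = 48% would fall before Day 30, with a mean of 8 uncovered days. The planning rates imply a later hazard of (7.1% − 6%)/335 = 0.0000328 per day. Expected missed events would be 87 × 0.484 × 8 × 0.0000328 ≈ 0.01, or about 0.1 at ten times that hazard.

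**The case against.** The strongest reply is that events are not tied to visits. Adverse events are assessed at the procedure, at discharge and at each visit (protocol Table F-2) and collected throughout the study (F.6.2). SAEs are due within 3 calendar days of site awareness (Table F-4). SAP 7.2 places events by onset date with no visit window, so a later attended visit can still reveal an earlier MDE. Access and deployment failure is settled at the procedure. Subjects declared lost to follow-up are exited and then fall under the last-seen clock. The 183-day rate is descriptive only. All of this stands, and it confines the problem to still-enrolled subjects with no contact or report between their last visit and the cut. It does not remove it, because nothing obliges a site to exit a silent subject by a given date. The tipping-point analysis in SAP 7.4 is optional and names only the primary endpoint.

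A reader might infer that the cut-date rule also corrupts the 30-day primary endpoint, or that Days 16–30 go wholly unassessed. The documents do not support either reading. The 1-day minimum is what operates there. The gap is at most 15 days, for subjects seen on Day 15–29 with no later contact or report before the cut. Such a cut is possible, since "The primary endpoint analysis will be completed upon 87 evaluable subjects reaching the 30 day endpoint", but on the planning rates few events would be lost.

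**Conclusion.** The point holds for the 183- and 365-day columns. The cut-date clock lets a still-enrolled subject with missed visits count as MDE-free without confirmed contact. At a 183-day summary the same applies to an international subject with no mandatory 6-month visit and no later contact before the cut. The direction is certain: the rate can only be lowered. The size is not established, because u and s are assumed. With u = 10, the 1-year false-pass risk exceeds the nominal 0.05 in every case shown, but only slightly (0.054 to 0.057) when s is near 0.85.

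At 30 days the cut-date clock matters only because raising the minimum to 30 days would not, by itself, require observation to Day 30. It would be tempting to call the confirmatory tests invalid, or the change indispensable before any analysis. The documents do not show enough unseen subjects or missed events for that. Severity is moderate.

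**What to change.** In SAP 7.9, define duration in study for every subject as index procedure to last documented contact or AE/status assessment, whether by visit, imaging, telephone or record check. Apply it to the 183- and 365-day columns and to the non-image rates that follow Table 5.

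For the 30-day column, change the duration rule and the 1-day minimum together, so that an MDE-free subject needs documented status on or after Day 30. For 1-month visits held on Day 15–29, obtain that status from existing records or a telephone check before lock.

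The change has a bias of its own. Failures always stay in m, while unconfirmed event-free subjects leave k, which can push the rate up. For example, 7/87 passes (p = 0.023), but with 5 unconfirmed successes removed, 7/82 does not (p = 0.038). Report the number excluded and, as a sensitivity analysis, the result with them counted as MDE-free.

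The cost is a short SAP amendment plus status checks. If visits are spread evenly over Day 15–45, about half of subjects (48%) may need a check. Some may become non-evaluable if their status cannot be confirmed. The margin between 100 enrolled and 87 evaluable is 13, so its adequacy depends on most checks succeeding.
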